Mapping involves walking around a community with local leaders, identifying all households, drawing a map, and randomly selecting the first household. Subsequent households are selected the same way as "spin-the-bottle." If a pre-existing list is available, then households can be selected at random before arriving at the cluster.

Respondent Selection (within a Household)

In all cases adult women and men will be interviewed, and in all cases only one eligible women or man will be interviewed per household. They will be asked specifically about their own health experience or, in the case of men, also about the health of their wives or partners. They will be asked about the health experiences of one of their children. Specific studies will first choose from the following adults to interview:

- 1. Mothers of young children
- 2. Fathers of young children
- 3. Women of reproductive age (15-49 years)
- 4. Men of reproductive age (15 years and older)

IRB Research Plan for New Data Collection

For studies that interview parents of young children, adult respondents will be narrowed to parents of children of specific age groups or children who were ill during the previous 2 weeks. Information will only be collected from parents of children younger than 60 months. Information will be only collected about one child per age group per household and only one child per illness group per household. The following are possible age and illness groups:

0–5 months	12–23 months	With fever in previous 2 weeks
0–11 months		With diarrhea in previous 2 weeks
0–23 months	6–23 months	With fast or difficult breathing in the previous 2 weeks
0–59 months	2–59 months	

For example, if a study needs information on excusive breastfeeding of children 0–5 months of age, immunization coverage for children 12–23 months, mothers' decision making regarding immunization, and fathers' decision making regarding immunization, the study would include respondents who are mothers of children 0–6 months of age, mothers of children who are 12–23 months of age, and fathers of children who are 12–23 months of age.

For surveys that include anthropometry (specifically, weight of children 0–59 months, height of children 24–59 months, and length of children 0–23 months), children 0–59 months whose mothers are interviewed will be weighed and have their height or length taken.

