For studies that interview women and/or men ages 15–17 years, consent will be obtained from an adult in the household to conduct the interviews or, in the case of emancipated minors (according to local legal definition), they will give their own consent.

Households within each sampled cluster will be visited by the data collectors. Interviewers will ask to speak to an adult (18 years of age or whatever the local legal age of majority is), and if available the interviewers will ask screening questions (and fill out a screening form) to determine whether an eligible mother or father is present in the household. The screening form will be destroyed at the end of the fieldwork. If the answer is yes, and he or she is home and he or she agrees to participate following an informed consent/assent process, then he or she is interviewed. If he or she is not home but expected back within 30 minutes, the interview team will return to the house no more than three times before finishing all the interviews in the area. If unavailable, he or she will be counted as "Non-response" and substituted with someone from another household.

When no eligible mother or father is available in a household, then the interview team proceeds to the next house selected to be visited. If a mother has more than one child age 0–59 months, normally they will be asked about the youngest child. However, for some countries, it can be predetermined to select one of the mother's children at random.

Sample Size Determination

Specific sample sizes will vary from country to country. However, sample sizes will be calculated to provide estimates with confidence levels of 95 percent and precision of 10 percent for key indicators. For stratified random sampling and LQAS the design effect is 1. For 30-cluster sampling a design effect of 2 will be assumed. For all cases, if indicators are to be disaggregated, the total sample size must be multiplied by the number of disaggregation categories; if parallel sampling is needed the sample size must be increased to ensure adequate sample sizes for all indicators collected. Final sample sizes will be powered on the most important indicators, which may result in wider confidence intervals for a few of the other indicators.

For individual studies, decisions will be made regarding the most important indicators for which to collect information. The sample size will be powered for these indicators. After this the study will use the

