Weight and height will be taken of children either 0–59 months or 0–23 months only where the mother was interviewed; where the father was interviewed; anthropometric measurements will not be taken. The same six steps will be followed for children. Only one child will be measured for households. Thus, for surveys that include anthropometry, the sample size will be calculated for them separately from the sample size calculated for the adult respondents.

Participants

Study participants will be from areas where MCSP is implementing programs and in some cases from control areas where MCSP is not working. Participants will be from the following groups:

- 1. Mothers of young children
- 2. Fathers of young children
- 3. Women of reproductive age (15–49 years)
- 4. Men of reproductive age (15+ years and older)
- 5. Children 0-59 (for anthropometry, specifically weight and height) of mothers who are being interviewed

Respondents will be adult women and men. However, for surveys that focus on child health or maternal and newborn care (MNC) a subset of women and/or men will be interviewed who have children of specific age groups, illness categories, or, in the case of MNC women (or wives/partners) who have delivered in the last 2 years, 1 year, or 6 months.

If anthropometry is collected from children, then children 0–59 months whose mothers are interviewed are also participants. Only one child per household will be measured. Amendments for specific studies will describe methodologies used to train data collectors on anthropometric measurement.

Inclusion or Exclusion Criteria

Only one adult woman and/or one adult man will be selected in a household where there are multiple eligible participants. Anthropometric data (length, height, and weight only) will be collected from only one child of the mother being interviewed. Study participant women and men will provide oral consent and will be informed that they do not have to answer all questions and can end the interview at any time. Mothers will provide oral consent for anthropometric measurements to be taken from the chosen child.

See section on selecting the respondent in a household for additional details.

4. Study Procedures

Recruitment Process

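### The youngest-child default leaves older under-five siblings out of any indicator defined on all children 0–59 or 2–59 months, and no weighting is stated to allow for it

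*Protocol*

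**What the plan says.** All references are to the protocol, section 3.

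- **Default child.** Respondent Selection (within a Household) states: "If a mother has more than one child age 0–59 months, normally they will be asked about the youngest child". An exception follows: "However, for some countries, it can be predetermined to select one of the" mother's children at random. No criterion is given for using the exception, and no weights go with it.
- **Target groups.** The same subsection lists possible age groups that include 0–59 and 2–59 months, and illness groups for the previous two weeks. It adds: "Information will be only collected about one child per age group per household and only one child per illness group per household".
- **Anthropometry.** Respondent Selection says that "children 0–59 months whose mothers are interviewed will be weighed and have their height or length taken". Under For Anthropometry the range may be narrower: "Weight and height will be taken of children either 0–59 months or 0–23 months only where the mother was interviewed". Only one child is measured ("Only one child per household will be measured", under Participants). Inclusion or Exclusion Criteria calls this "Mothers will provide oral consent for anthropometric measurements to be taken from the chosen child" without saying how the child is chosen.
- **Precision.** Sample Size Determination plans for 95% confidence and ±10 points.
- **Tabulation examples.** Those in section 4 (Study Implementation, item 4) concern mothers of children 0–23 months and their youngest or last-born child.

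**The concern.** When an indicator's denominator is every child 0–59 or 2–59 months, taking the youngest child is not a neutral way to pick one per mother. A three-year-old with a baby sibling cannot enter the sample; a three-year-old without one can. This has two effects. The age mix shifts toward younger children, which moves any indicator that varies with age. The older children who remain are those whose mother has had no later surviving birth, so an estimate for 24–59 months is conditioned on birth spacing. Weighting cannot restore children whose selection probability is zero.

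The secondary objectives are about change, and surveys are to be repeated. Pregnancy spacing is itself one of the modules. If spacing lengthens between rounds, the sampled age mix changes with it, and part of an apparent trend could come from the selection rule. Countries that use the random option would also not be comparable with those that use the default.

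**Working it through.** **1. The plan's own figures.** 1.96² × 0.5 × 0.5 / 0.10² = 96.04, stated as 96; with a design effect of 2, 192. Both reproduce. They set the ±10-point yardstick and are not changed by this point.

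**2. Inputs not in the documents (assumed).**
- Birth interval: 9 months plus a lognormal time with log-SD 0.5, median interval 27 to 48 months.
- Share of mothers with no further birth, *s*: 10% to 60%.
- All under-fives: uniform in age over 0–59 months.
- Stunting: 15% at birth, rising linearly to 40% at 24 months, then flat. The true 0–59 month value is 0.4 × 27.5% + 0.6 × 40% = 35.0%.
- Diarrhea: 12% at 0–5 months, 24% at 6–23, 15% at 24–35 and 9% at 36–59. The true value is 0.1 × 12% + 0.3 × 24% + 0.2 × 15% + 0.4 × 9% = 15.0%.

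**3. Formula.** A child aged *a* months is the mother's youngest with probability S(a) = s + (1 − s) × P(interval > a). The youngest-child sample has age density proportional to S(a) instead of uniform. For example, with median 27 months, s = 0.1 and a = 36: P(interval > 36) = 1 − Φ(ln(27/18)/0.5) = 1 − Φ(0.811) = 0.209, so S = 0.1 + 0.9 × 0.209 = 0.288.

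**4. Results.**

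| Median interval, *s* | Under-fives dropped | Sample share 0–11 mo (true 20%) | Sample share 48–59 mo (true 20%) | Mean age (true 30.0) | Stunting (true 35.0%) | Diarrhea (true 15.0%) |
|---|---|---|---|---|---|---|
| 27, 10% | 46.2% | 37.2% | 4.9% | 18.9 | 30.8% | 18.3% |
| 33, 20% | 32.9% | 29.8% | 8.5% | 22.7 | 32.6% | 17.2% |
| 33, 40% | 24.7% | 26.6% | 12.3% | 25.1 | 33.4% | 16.5% |
| 40, 40% | 18.6% | 24.6% | 13.3% | 26.2 | 33.9% | 16.1% |
| 48, 60% | 8.8% | 21.9% | 16.6% | 28.3 | 34.5% | 15.5% |

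The share of children kept, by age, across these scenarios is 100% at 0–11 months, 89–100% at 12–23, 46–95% at 24–35, 21–85% at 36–47 and 13–76% at 48–59. Averaging the last three bands, (46 + 21 + 13)/3 = 27% to (95 + 85 + 76)/3 = 85% of children 24–59 months are kept, so about 15–73% are lost. Children 12–23 months gain sample share almost as much as infants: 33.2% against 37.2% in the first row. The tilt is therefore toward children under about 24 months.

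**5. A second model.** Gamma birth intervals (mean 27, 33 and 40 months; SD 9, 12 and 15), 1–6 births per mother and 400,000 simulated mothers give 62%, 52% and 42% of children 24–59 months lost. With a steeper assumed stunting curve (10, 20, 40 and 45% at 0–5, 6–11, 12–23 and 24–59 months), stunting is understated by 4.4, 3.3 and 2.4 points. The direction is the same, and the size falls within or close to the range above.

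**6. Random choice instead.** In the shortest-interval setting, simulated mother by mother, the true 0–11 month share was 18.0%. Unweighted random choice gave 15.8% and the youngest-child rule 35.1%. Mean ages were 31.3, 32.0 and 19.6 months. The small remaining gap with random choice is what weighting by the number of eligible children removes.

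**The case against.** The strongest reply is that the protocol mostly selects by the child's age or illness group. Respondent Selection limits respondents to parents of children in specific groups. Sample Size Determination works an example with separate samples of mothers for 0–5 and 12–23 months, and requires parallel sampling under LQAS or stratified sampling when indicators come from different child groups. On that reading the youngest-child sentence only breaks ties within a group. This stands. A reader might infer that a 12–23 month child with a newborn sibling can never be selected, or that the youngest-child sentence flatly contradicts the one-child-per-group rule. The text does not support either: such a child is what makes the mother eligible in a 12–23 month sample, and the two sentences can be reconciled. The reply does not help a survey with a single 0–59 or 2–59 month group, because a within-group tie-break on the youngest drops every older sibling there.

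A reader might also infer that the youngest child is the one measured. That is a natural reading, but the protocol says only that one chosen child is measured, so the anthropometry rule is unspecified. Where measurement is limited to 0–23 months the effect is small in any case.

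Finally, the default is qualified by the word normally, random selection is already allowed, study amendments must state the options chosen, and every tabulation shown fits the youngest-child rule. All true. What remains missing is a criterion for choosing the random option, and weights.

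**Conclusion.** The concern holds for indicators whose denominator is all children 0–59 or 2–59 months. For these, the default excludes every under-five with a younger under-five sibling, without weighting or a restricted label on the denominator. Under the assumed spacing and age curves, about 9–46% of under-fives are dropped. Stunting is understated by about 0.5–4 points and diarrhea overstated by about 0.5–3 points.

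The bias is moderate. It is smaller than the ±10-point precision and depends on birth spacing that the documents do not give. The age-mix part vanishes for an outcome that is flat in age, although selection of older children on birth spacing would remain. No sample size removes it. The possible drift between rounds follows from the mechanism but has not been quantified.

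Last-birth indicators fit the rule, and those for 0–5, 0–11 and 0–23 months are little affected. The 12–23 month group is unaffected if selection follows the per-age-group rule. The anthropometry figures apply only if the measured child is in fact the youngest.

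**What to change.** In Respondent Selection (within a Household), state that the child is selected within the indicator's age or illness group, and then:

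- For 0–59 and 2–59 month indicators, and for 0–59 month anthropometry, select one eligible child at random, record how many were eligible, and weight by that number.
- Record the count on the questionnaire, because the screening form is destroyed after fieldwork.
- Where weighting is not workable, as with hand tabulation or LQAS decision tables, label the denominator as the youngest child under five.
- Keep the youngest-child rule for last-birth indicators (antenatal care, IPTp, net use in pregnancy, facility birth).
- Say under For Anthropometry how the measured child is chosen.
- Keep the same rule across survey rounds in a country.

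The cost is a wording change, one extra variable, a weight and a small loss of precision. Random selection is already permitted, so no new field method is needed.

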appropriate sample size formula based on the chosen sampling methodology. The value of p (proportion) should be .5 (50%) given that these surveys collect information from a variety of indicators with varying proportions in a population, many of which may not be known before the survey is implemented. A p value of .5 gives the maximum sample size needed to estimate any level.

The sample size for a single survey designed to estimate levels at one point in time (not compared with another group) will be determined by the following:

For stratified sampling, simple random sampling, and LQAS:

$$N = Z\alpha^2 pq / d^2$$

- $Z\alpha = 1.96$ corresponding to a confidence level of 95%
- p = 0.5 (maximum sample size)
- q = 1 0.5 = 0.5
- d =accuracy desired = 10% = 0.10
- $N = (1.96)^2 \times 0.5 \times 0.5 / (0.10)^2 = 96$

For 30-cluster sampling, samples size collected from the preceding formula will be multiplied by 2:

$$N_C = N \times \text{deff}$$

Thus, $N_C = 192$

The number of households visited will be calculated based on estimates of the percentage of families expected to have children in the needed age groups. For example, if it is estimated that 45 percent of households have children 0–23 months and 166 eligible mothers must be interviewed, then survey teams may have to visit N_1 =166 × (100 / 45) = 369 households.

Sample sizes for comparison of two phases or groups will use the following formula for stratified random sampling or simple random sampling:

$$N_1 = N_2 = [Z\alpha_{1/2} + Z\beta]^2 [2pq] / (p1 - p2)^2 = [1.96 + 1.28]^2 [2(.5)(.5)] / (.2)^2 = 1.31$$

- N_1 = baseline sample size
- N_2 = final evaluation sample size
- $Z\alpha_{/2}$ is the Z value corresponding to the chosen level of risk α . ($Z\alpha_{/2}$ should be used in two-sided tests, and $Z\alpha$ should be used in one-sided tests.)
- $Z\beta$ is the Z value corresponding to the chosen level of risk β (it directly relates to the "power" of the test as power = 1β ; ($Z\beta$ = 1.28 for a power of .9)
- p_1 is the expected coverage at baseline (can be set to .5 for maximum sample size)

•
$$q_1 = 1 - p_1$$

• p_2 is the expected final coverage (can be set to .5 for maximum sample size)

•
$$q_2 = 1 - p_2$$

- $p = (N_1 p_1 + N_2 p_2) / (N_1 + N_2)$
- q = 1 p

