For 30-cluster, the final value calculated from the preceding formula is multiplied by 2 (design effect) for a sample size of 262. If it is estimated that 45 percent of the households will have eligible mothers, then the total number of household that must be visited is $N_{1\ell} = N_{2\ell} = 262 \times (100 \ / \ 45) = 582$

Next, if cluster sampling methodology is used, a decision will be made to either to increase the total number of interviews in order to disaggregate into the needed age and illness groups of the children or to use parallel sampling. For example, if information is needed on exclusive breastfeeding of children 0-5 months of age and immunization coverage of children 12-23 months, the sample size as determined by the formula could be multiplied by 4 in order to have enough children 0-5 months to provide exclusive breastfeeding estimates with confidence levels of 95 percent and precision of 10 percent. So, if the original estimate is 210 then the actual sample size will be 840 (4 × 210). However, if parallel sampling is used, then 210 mothers of children 12-23 months and 210 mothers of children 0-5 months should be interviewed for a total of 420 mothers interviewed. In this case it is only necessary to multiple the *n* calculated from the sample formula by 2.

Parallel sampling is especially useful for cluster sampling when information is needed about indicators with different denominators, such as for the following:

Indicator	Denominator
Exclusive breastfeeding of children 0–5 months	Children 0–5 months
Immunization coverage of children 12–23 months	Children 12–23 months
Decision making of mothers	Mothers
Decision making of fathers	Fathers

If LQAS or stratified random sampling methodologies are used, parallel sampling must be used if information is collected for indicators from different age and illness categories of children.

Specific studies will arrive at sample sizes though the following steps. Decisions made will be part of individual study protocols. The steps are as follows:

- 1. Decide on most important indicators.
- 2. Choose appropriate sample size formula.
- 3. Use p = .5.
- 4. Calculate sample size based on appropriate formula.
- 5. If using cluster methodology, decide between inflating the total sample size to allow disaggregation into appropriate age and illness groups or using parallel sampling.
- 6. Adjust the calculated sample size number by needed disaggregation or to collect parallel samples.

For Anthropometry

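### Multiplying the sample by the number of categories secures ±10 points per category only for equal-sized or quota-filled groups, and conflicts with the protocol's own ×4 example

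*Protocol*

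**What the plan says.** All the relevant text is in Protocol section 3, under Sample Size Determination.

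- **Precision target:** "sample sizes will be calculated to provide estimates with confidence levels of 95 percent and precision of 10 percent for key indicators". The formula that follows uses d = 0.10, so the target is ±10 percentage points.
- **General rule:** introduced as applying to all cases, "if indicators are to be disaggregated, the total sample size must be multiplied by the number of disaggregation categories". Parallel sampling is dealt with in a separate clause, which asks only for an adequate increase.
- **Design effects:** "For 30-cluster sampling a design effect of 2 will be assumed", and "For stratified random sampling and LQAS the design effect is 1".
- **Worked example for cluster surveys:** exclusive breastfeeding is wanted for ages 0–5 months and immunization coverage for ages 12–23 months. If the total is inflated, "the sample size as determined by the formula could be multiplied by 4 in order to have enough children 0-5 months" at the stated confidence and precision, taking 210 to 840. If parallel sampling is used, 210 mothers are interviewed for each group, 420 in all, and the factor is 2.
- **Restriction:** LQAS and stratified surveys must use parallel sampling when indicators come from different age or illness groups of children.
- **Tolerance:** wider intervals are accepted for a few indicators other than the most important ones.

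The six closing steps tell each study to inflate or use parallel samples, but give no factor.

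**The concern.** The general rule and the example attach the category count to different options. The rule multiplies by the count whenever results are to be broken down. The example uses the count (2) only where each group is filled to its own target, and a larger factor (4) where the total is inflated and children fall into groups as they come. A survey with two groups of unequal size and no quotas cannot follow both.

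The rule is worded as mandatory; the example is worded as a possibility. An annex author who relies on the rule would size the survey too small for its smallest group and could still describe that group's estimate as meeting ±10 points. The groups at risk are those that carry key indicators, with exclusive breastfeeding at 0–5 months the protocol's own case. A shortfall cannot be repaired once fieldwork is over.

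**Working it through.** **Inputs from the Protocol:** Z = 1.96, p = q = 0.5, d = 0.10; design effect (deff) 2 for 30-cluster surveys and 1 otherwise; base 210 in the worked example.

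**Input assumed:** children aged 0–5 months are 6/24 = 25% of those aged 0–23 months, taking ages as evenly spread. The Protocol does not state this share, but it is what makes ×4 the right factor. A range is shown below.

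**1. The plan's own figures reproduce.**
- N = 1.96² × 0.5 × 0.5 / 0.10² = 96.04 (stated 96); with deff 2, 192.08 (stated 192).
- 4 × 210 = 840, and 840 × 0.25 = 210 children aged 0–5 months. Half-width = 1.96 × √(2 × 0.25 / 210) = 9.6 points, so the target is met.
- 2 × 210 = 420 under parallel sampling, again 210 per group and 9.6 points.

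**2. What a category count gives in general.** With k categories and no quotas, a category with share s receives k·s·N interviews. If N only just meets ±10, the half-width is 10/√(k·s) points. This exceeds 10 whenever s is below 1/k. With two categories, a smaller share of 40% gives ±11.2, 25% gives ±14.1 and 10% gives ±22.4. The factor that restores ±10 is 1/s.

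**3. The rule applied to the protocol's example** (30-cluster, no parallel sampling, s = 25%, deff 2):

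| Factor | From 210: total, aged 0–5 months, half-width | From 192: total, aged 0–5 months, half-width |
|---|---|---|
| ×2 (two named groups) | 420, 105, ±13.5 | 384, 96, ±14.1 |
| ×3 (6–11 months counted too) | 630, 157.5, ±11.0 | 576, 144, ±11.5 |
| ×4 (the example) | 840, 210, ±9.6 | 768, 192, ±10.0 |

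For ×2 from 210: 1.96 × √(2 × 0.25 / 105) = 0.135.

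**4. Sensitivity of ×2 from 210.**
- Share, at deff 2: 20% (84 children) gives ±15.1; 30% (126) gives ±12.3; 35% (147) gives ±11.4. The target is met once the share reaches 192/420 = 45.7%.
- Design effect: assume deff 2 holds at 210/30 = 7 interviews per cluster. Then 1 + (7 − 1)ρ = 2, so ρ = 1/6. With 105/30 = 3.5 children per cluster, deff = 1 + 2.5/6 = 1.42 and the half-width is ±11.4. At deff 1, 105 children would give ±9.6.

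**The case against.** The strongest reply is that the protocol already handles the case that matters. Its example inflates to 840 precisely so that the 0–5 month group reaches the target, and the closing steps do not repeat the category count. Country sampling plans go to the IRB as amendments, and no annex is shown using the short rule. This stands in part: a survey that follows the example meets the target, so the shortfall is a risk for annexes that follow the rule, not something shown to have happened. It does not remove the conflict, because the rule is the only general instruction that gives a factor, and it claims to cover all cases.

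Two other defences are weaker. The ×4 would agree with the rule if 0–23 months were four six-month bands, but the example names two groups and the protocol's list of age groups contains no such set. The tolerance for wider intervals covers other indicators, not those the survey is sized for.

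A reader might infer more than the documents support:

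- **That the protocol prescribes 420 interviews without quotas for its own example.** It does not; 420 appears only under parallel sampling, with 210 per group.
- **That stratified or LQAS surveys would report child age groups at about ±14** (96 × 2 = 192 interviews, 25% share, 48 children, deff 1). Parallel sampling is compulsory there, so this can arise only for other unequal breakdowns without quotas.
- **That ×2 works only if both groups are exactly 50%.** That is so from a base of 192 or 96, but from 210 a share of about 46% is enough.
- **That the half-widths are firm.** They rest on assumed shares. Mothers are normally asked about the youngest child, which may raise the 0–5 month share, and the design effect may fall in a small subgroup. Both narrow the gap; neither closes it over the ranges of 20% to 35% for the share and 1.4 to 2 for the design effect, each varied separately.

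**Conclusion.** The general rule is wrong as written for categories of unequal size that are not filled by quota, and it conflicts with the worked example in the same section. On that example in a 30-cluster survey without parallel sampling, ×2 from 210 gives about ±13.5 points for ages 0–5 months instead of ±10, assuming a 25% share and the protocol's design effect of 2. The range is ±11.4 to ±15.1 for shares of 35% down to 20% at design effect 2, and about ±11.4 at a 25% share if the design effect falls to about 1.4.

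The rule is correct where categories are about equal or each is filled to a fixed number. Exposure is therefore mainly in 30-cluster surveys that inflate without parallel sampling and follow the rule rather than the example. In the other designs it is limited to unequal breakdowns outside child age and illness groups.

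**What to change.** Replace the general rule in Sample Size Determination with two cases and a fallback:

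1. **Total inflated without quotas:** multiply the formula size by 1/(expected share of the smallest category for which a key indicator is to meet ±10 points). Cite the existing ×4 as the illustration (1/0.25), and state the 25% share there as an assumption.
2. **Each category filled to its own target** (parallel sampling, quotas or fixed allocation to strata): multiply by the number of categories.
3. **Neither done:** the annex states the half-width actually expected for each category instead of ±10.

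The second case must stay. Applying 1/share everywhere would overshoot: two strata sampled at 96 each need 192 interviews even if one is 10% of the population, whereas 1/0.10 would ask for 96 × 10 = 960. Limiting the first case to key indicators keeps the existing tolerance for wider intervals on a few others.

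In the generic protocol this is a short wording change and adds no new method. For a survey like the example, an annex that would have used ×2 without quotas has three choices: 840 interviews; parallel sampling at 420, with teams screening until the 0–5 month target is filled; or 420 without quotas and an openly stated wider interval.
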